7.3 ADDITIONAL STATISTICAL MODELS

¹ MLM goes by many aliases in the social and behavioral science literature, including but not limited to: hierarchical linear modeling (HLM), linear mixed effects modeling, mixed modeling, and random effects modeling. Though some of these terms denote slight distinctions by subfield, each is more or less the same. I will use multilevel modeling, or MLM, throughout my documentation.

As noted in the published protocol paper, we will also examine brooding as a mediator of the relation between treatment condition and stress. We will harness a path modeling approach. In this path model, we will lag the effect such that treatment associates with 4-week stress, mediated by baseline brooding, and so on (see Figure 1). Path modeling will be completed using the *lavaan* package in R (Rosseel, 2012). Mediation effects will be calculated using bootstrapped 95% confidence intervals.

[figure not shown]

Figure 1. The proposed path model that will allow us to explore the extent to which brooding mediates the relation between treatment and perceived stress (PSS). Subscripts indicate each time point (B = Baseline; 4, 8, 12 = 4-, 8-, and 12-weeks, respectively). Single-headed arrows connecting two variables indicate regression pathways. Two-headed arrows indicate covariance. Single-headed arrows on a single box denote unmeasured endogenous variance.

We will also explore the relation between app usage and each outcome through a series of MLMs. The MLM parameters will be similar to the primary model (described previously). One MLM will be run for each primary and secondary outcome (brooding, perceived stress, loneliness, optimism, sleep disturbance), predicted by app usage. We will define the usage variable as: (Number of activities completed) / (Total number of days active on the app). This approach accounts for how involved participants were with the treatment while controlling for continued usage. We will parse usage into between- and within-person effects (see Carpenter et al., 2016). Between-person usage will be a Level-2 variable, indicating each participant's usage over the entire number of active days in the study, whereas within-person usage will be at Level-1, indicating the amount of app usage (relative to days active) between assessments.

NCT 0456788 – Statistical Analysis Plan

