**d. Nature of Study:** The nature of this study is confirmatory and exploratory. We will be testing the hypothesis that using the Happify platform will result in greater decreases in perceived stress and rumination over an 8-week period compared to a waitlist control, with users who complete more activities experiencing more improvement. We also aim to explore the effects of Happify on several factors, including: sleep disturbance, loneliness, and optimism. To do this, we will employ a longitudinal randomized design. Participants will be randomly assigned to either the Happify experimental condition or the waitlist control condition after meeting inclusion criteria and taking a baseline assessment. Those in both conditions will be asked to complete assessments at 4 weeks (mid-point), after the 8-week intervention period (immediate post-test), and 1-month post intervention. Participants will be adolescents aged 13-17 with elevated levels of rumination and stress who are recruited online.

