- ii. The Qualtrics prescreener link will then be sent to the child. It includes verifying their country of residence, age, and previous Happify use. They will also complete the Perceived Stress Scale (PSS) and Ruminative Responses Scale (RRS) to ensure their scores are above thresholds (PSS  $\geq$  10; RRS  $\geq$  14). Finally, the participant must agree to study duties, including: completing the baseline assessment, completing activities via Happify through a computer or smartphone, and being contacted throughout the 12 week period by Happify research staff. Participants are told that they may be assigned to a waitlist control and will not have access to the Happify platform until the end of the study but will still have to complete assessments. They are asked to check a box if they would be willing to continue with the study and not download Happify if assigned to the waitlist. We will ask participants to agree to not discuss the study with friends or family also participating in the study. If the child meets the inclusion criteria, they will be instructed that they'll receive an email inviting them to complete the first assessment (baseline assessment) on the following Monday or Thursday (whichever comes first). They must complete this assessment in order to qualify for the study, and must continue to meet thresholds for perceived stress and rumination, and pass at least one of 7 attention checks during the baseline assessment. This email will have instructions to set up a unique study ID that will be used throughout the study to link participant data across assessments and other data collections.
- iii. In this email, participants will be provided an assent form (through Qualtrics) which is shown at the beginning of the baseline assessment. If participants choose to, they will read and agree to a statement that they will provide honest and thoughtful responses throughout the study, and a separate statement agreeing not to discuss the study with any family or friends who may also be participating in the study. Participants must complete the baseline to be randomized to condition. Participants are

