required to pass at least one of the attention checks in the baseline assessment. These attention checks require people to select a specific response option (e.g., for the PSS, an attention check item could instruct the participant to select “Never”, and this would vary across all assessments). Participants who complete and pass the baseline assessment on Qualtrics will be randomly assigned, via a Qualtrics randomization tool, to either the experimental or waitlist control group, and will receive an email or text (through Simple Text) with information detailing their condition on their corresponding start date. If they are in the experimental condition, they will also receive a link to download Happify. Both groups will complete assessments at 4 (mid-point), 8 (immediate post-intervention), and 12 weeks (one month post-intervention) via their preferred method of contact which was obtained in the baseline (e.g. email or text). All participants will be prompted to provide their user ID and complete the PSS, RRS - Brooding Subscale, LOT-R, PROMIS Pediatric Sleep Disturbance scale, and the RULS-8 via Qualtrics at each assessment point. Participants will also be asked at each assessment point if they have sought out help from other online platforms and what their current schooling situation is (fully remote, hybrid model, fully in person, home-schooled, or not in school). All of the assessments will have one attention check per questionnaire, which will instruct participants to select a specific response option to ensure they are reading questionnaire items and instructions carefully. The SLSS and PANAS-C-S will be administered only during baseline for scale validation purposes, and the experimental group will receive the Happify scale as part of the app experience every 2 weeks. In both cases, participants who do not qualify for the study will be thanked and alerted through Qualtrics that they do not qualify, and all their survey information will be deleted to protect their confidentiality. Participants who do not complete the baseline assessment will not go onto the study and will also have all of their information deleted.

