#### **e. Design and Proposed Statistical Analysis**

**I. Changes in Stress and Secondary/Exploratory Outcomes:** To assess whether changes in participants' perceived stress differed across the two groups, we plan to conduct a 2 (group: intervention vs. control) x 4 (time: baseline, 4 weeks, 8 weeks, 12 weeks) repeated-measures ANOVA on participants' PSS scores, controlling for participant age and gender. Similar analyses will be conducted on secondary and exploratory outcome measures. To determine whether usage predicted changes in these outcomes, we will also conduct regression analyses among participants in the intervention condition regressing their scores on each outcome variable onto the number of activities completed within the Happify for Teens platform, while controlling for corresponding baseline scores on that outcome.

ii. **Rumination as a Potential Mediator:** To test whether any observed changes in perceived stress can be attributed to changes in brooding, we also plan to conduct mediation analyses using Hayes' PROCESS macro for SPSS.

iii. **Data Exclusion:** Because careless responding is problematic with online surveys and may artificially increase relationships between variables, we plan to use two separate a priori mechanisms for identifying low quality data: (1) failing 3 or more attention checks in an assessment, and (2) completing an assessment at a rate faster than 1 second per item. We will then re-run the analyses described above without these participants to test whether effects differ when removing low quality data.

iv. **Happify Scale Validation:** To validate the scale for internal purposes, we will conduct confirmatory factor analysis testing the two-factor structure of the scale, and examine convergent validity by computing correlations between the positive emotion subscale and the PANAS-C-S and between the life satisfaction subscale and the SLSS that are collected at baseline.

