3 ANALYSIS OBJECTIVES

The primary objective of this study is as follows:

- Comparing the Happify for Teens condition and the waitlist control groups, examine changes in perceived stress and rumination (brooding) across baseline, 4-weeks, 8-weeks (post-intervention), and 12-weeks.

The secondary objective of this study is as follows:

- Comparing the Happify for Teens condition and the waitlist control groups, examine changes in loneliness, optimism, and sleep disturbance across baseline, 4-weeks, 8-weeks (post-intervention), and 12-weeks.

The exploratory objectives of this study are follows:

- Determine the extent to which brooding mediates the relation between treatment condition (Happify for Teens vs. control) and perceived stress.
- Among those in the Happify for Teens treatment, we will explore the extent to which app usage (i.e., number of activities completed, number of active days) associates with each of the five outcome variables from the primary and secondary objectives.

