5 ENDPOINTS AND COVARIATES

The primary criterion of interest will be perceived stress scores, self-reported at baseline, 4-week midpoint, 8-week post, and 12-week follow-up. The secondary criterion of interest will be brooding scores at the same time points. Additionally, three exploratory outcomes will be examined at the same time points: optimism, sleep disturbance, and loneliness. The effect of the Happify treatment will be examined for each outcome.

In each model, we will covary the effects of participant age, gender, and race. Gender will be coded into two binary variables (0 = man or other, 1 = woman; 0 = woman or man, 1 = other). Race will be coded into a single binary variable (0 = White, 1 = all other races). Given that individuals who identify as White comprise almost 75% of the sample, this coding scheme prevents saturating each model with a large number of dummy codes while still preserving much of the racial distribution of the sample.

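### The first lag of the mediation model uses brooding measured before randomisation as the mediator, so that indirect effect is zero in expectation whatever the app does

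*SAP*

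**What the plan says.** SAP section 3 lists mediation as an exploratory objective: "Determine the extent to which brooding mediates the relation between treatment condition (Happify for Teens vs. control) and perceived stress". SAP section 7.3 plans a lagged path model in lavaan, with bootstrapped 95% intervals for the mediation effects, in which "treatment associates with 4-week stress, mediated by baseline brooding, and so on". Continued in the same way, 4-week brooding would mediate the effect on 8-week stress, and 8-week brooding the effect on 12-week stress. Brooding is available at all four assessments (SAP section 5: "The secondary criterion of interest will be brooding scores at the same time points").

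The protocol is consistent about the order of events. Section I.d describes assignment to the app or the "waitlist control condition after meeting inclusion criteria and taking a baseline assessment". Section II.a.iii says "Participants must complete the baseline to be randomized to condition" and "Participants who complete and pass the baseline assessment on Qualtrics will be randomly assigned". App access comes later still: "If they are in the experimental condition, they will also receive a link to download Happify".

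The protocol's mediation question, in section II.e.ii, is "whether any observed changes in perceived stress can be attributed to changes in brooding".

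**The concern.** A mediator of a randomised treatment has to be something the treatment can change. Baseline brooding is fixed before assignment. Under section II.a.ii it is also part of the eligibility check, because the rumination threshold must still be met at baseline. Nor is a baseline score a change in brooding, which is what the protocol asks about.

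The risk is a wrong statement about mechanism. An interval covering zero could be read as no mediation at 4 weeks, when the term could never have shown any. An interval excluding zero could be read as mediation, when it reflects baseline imbalance or selective dropout. If the lagged terms were summed into a total indirect effect (the SAP does not say that they will be), this one would contribute no information about mechanism.

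**Working it through.** The documents give no effect size, power or precision for the mediation analysis, so there is no figure of theirs to reproduce. The check is algebra, followed by simulation.

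**1. Algebra.** Let *a* be the effect of condition on the mediator and *b* the effect of the mediator on stress given condition. The indirect effect is *a* × *b*. With baseline brooding B0 as mediator, *a* = E[B0 | app] − E[B0 | waitlist] = 0 under randomisation, so *a* × *b* = 0 for any *b*.

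**2. Size of the noise.** With 400 per arm (Protocol section III, Sample Size) and B0 standardised, the baseline difference between arms has standard error √(1/400 + 1/400) = 0.071 SD. The estimated indirect effect therefore varies around zero with SD of about 0.071 × *b*. For an assumed *b* of 0.30 that is 0.021; for 0.40 it is 0.028.

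**3. Simulation over a range of app effects.** Inputs from the documents: 400 per arm and the order of assessments. Assumed: standardised scores, baseline-to-week-4 brooding slope 0.6, brooding-to-stress path 0.5, slope of 4-week stress on baseline brooding 0.3, residual SD 0.8, no direct effect, no missing data. There were 1,000 trials per row; percentile bootstrap intervals (200 resamples) were computed for 400 of them.

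| Assumed reduction in 4-week brooding | Expected mediated effect | Baseline-brooding term: mean (SD) | Interval excludes 0 | 4-week brooding to 8-week stress: mean (SD) | Interval excludes 0 |
|---|---|---|---|---|---|
| 0 | 0 | 0.0003 (0.021) | 5.0% | 0.0001 (0.029) | 4.75% |
| 0.2 | −0.2 × 0.5 = −0.10 | 0.0003 (0.021) | 4.75% | −0.098 (0.028) | 93.25% |
| 0.5 | −0.5 × 0.5 = −0.25 | 0.0004 (0.021) | 8.5% | −0.249 (0.033) | 100% |

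The last two columns adjust for baseline brooding. In this set-up the baseline-brooding term does not depend on the app effect, so the differences among its three rejection rates are simulation noise. Pooled, they are (20 + 19 + 34)/1,200 = 6.1%, roughly a false-positive rate.

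**4. Where the effect goes.** A further run of 2,000 trials used the same slopes of 0.6 and 0.5 and a mediated effect of −0.15 SD. The baseline-brooding term averaged 0.0008 (SD 0.021), and the direct effect of condition on 4-week stress averaged −0.150. An effect carried wholly by brooding was thus reported as wholly direct. The path through 4-week brooding to 8-week stress averaged −0.151 (SD 0.030). A separate run with the same −0.15 effect gave −0.0006 (SD 0.028) for the baseline term and −0.151 (SD 0.030) for the ordered path. Adjusting for baseline PSS as well as baseline brooding, as proposed below, also recovered −0.15.

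**5. Dropout.** SAP section 7.2 expects fairly high attrition, and section 7.3 names no missing-data method for the path model. With about 36% dropout, incomplete cases removed, and log-odds of dropout in the app arm rising by 0.3 or 0.5 per SD of baseline brooding (all assumed), the baseline term averaged −0.032 and −0.050 SD, against −0.001 without dropout.

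**The case against.** Figure 1 is not available in the text reviewed. Its caption mentions both regression and covariance arrows, so we cannot see how condition and baseline brooding are linked. If no path joins them, there is no product term and the fault is loose wording. That limit stands. But the sentence names baseline brooding as the mediator, a covariance would not turn it into a treatment effect, and a figure that disagrees with the text would itself need reconciling.

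Zero holds in expectation, among everyone randomised. With dropout that depends on baseline brooding differently by arm, the estimate can be systematically non-zero, as step 5 shows. This is right, and it means chance imbalance is not the only source of a non-zero result. It is a second reason not to interpret the term.

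The simulation inputs are assumptions, and the zero mean follows from algebra alone. Also fair: the SDs and the recovered effects depend on the chosen paths, and the figures are illustrative.

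The analysis is exploratory and the later lags, as implied, are correctly ordered. Both points stand and limit the weight of the concern, but neither repairs the first lag. Nothing elsewhere in the documents does.

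**Conclusion.** The concern holds as stated. The indirect effect of condition on 4-week stress through baseline brooding is zero in expectation because the mediator precedes randomisation, and it cannot answer the protocol's question about changes in brooding. This rests only on the order of events in the protocol and the wording of SAP section 7.3.

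The numerical contrast (about 0.000 against about −0.15 for the correctly ordered path) rests on assumed paths, no missing data and no unmeasured common cause of brooding and stress.

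One of the three lagged indirect effects implied by the SAP is affected. The other two and the primary treatment comparison are not. It should be corrected before the mediation results are reported.

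**What to change.** - Remove baseline brooding as a mediator. Enter baseline brooding and baseline PSS as covariates on every later variable in the path model.
- Define two indirect effects, each with a bootstrapped 95% interval: condition to 4-week brooding to 8-week PSS, and condition to 8-week brooding to 12-week PSS.
- Give 4-week PSS a direct treatment path only. If a 4-week mediation result is wanted, 4-week brooding could be used instead, labelled as contemporaneous and without temporal ordering.
- Make Figure 1 agree with the text, and state how incomplete cases are handled in the path model.

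The cost is SAP wording, the figure and a few lines of lavaan code; no new data are needed. The plan loses a lagged mediation estimate for 4-week stress, which this assessment schedule cannot provide. SAP section 2 shows that the data had already been extracted and merged, so the change should be dated, recorded as made after extraction, and justified by the design rather than by any result.

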7.2 PRIMARY STATISTICAL MODELS AND ASSUMPTIONS

Repeated measures data, particularly with relatively high amounts of attrition (i.e., missing data in the criterion), are effectively analyzed via multilevel modeling (MLM)¹. MLM has several advantages over traditional approaches, such as repeated measures (rm) ANOVA, the first of which is that rmANOVA assumes constant variance across treatment condition. Secondly, rmANOVA assumes sphericity (the within subject association between individual scores is equivalent across treatment conditions).

The MLM will be computed in R statistical software (R Core Team, 2022) and the *lme4* package (Bates et al., 2015) using REML estimation. Upon running the full model (see below), we will test the key MLM assumptions by examining residuals for linearity, normality, and homogeneity (Raudenbush & Bryk, 2002). We will also examine correlations between random and fixed effects. A significant correlation would violate the assumption of endogeneity, meaning that we would need to consider alternative approaches (McNeish & Kelley, 2019). The full MLM is depicted mathematically as follows (excluding age, gender, and race covariates),

$$PSS_{ti} = \gamma_{00} + \gamma_{01} \text{Condition}_i + \gamma_{10} \text{Time}_{ti} + u_{0i} + u_{1i} + r_{ti}$$

where t denotes repeated observations, i denotes unique individuals, γ_{00} denotes the grand mean of the outcome (fixed intercept), γ_{01} denotes the fixed effect of treatment condition (a Level-2 variable), γ_{10} denotes the fixed effect of time (a Level-1 variable), u_{0i} denotes a random intercept, u_{1i} denotes a random slope for time (allowing each individual to have a unique trajectory), and r_{ti} denotes residual error.

The first MLM will include a random intercept and no random slope. We will then compute the model with the random slope included (see the above equation) and conduct a likelihood ratio test using deviance statistics. If the difference in deviance is significant, we will conclude that the model with the random slope fits the data best. We will also create spaghetti plots to depict random effects in each criterion variable.

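### The between-person usage coefficient in SAP 7.3 mixes pre-existing differences between users with change, so it is a biased measure of whether heavier users improve more

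*SAP*

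**What the plan says.** The usage hypothesis in the protocol concerns change. Section I.d (Nature of Study) expects greater reductions in stress and rumination, "with users who complete more activities experiencing more improvement". Section II.e introduces the analysis with "To determine whether usage predicted changes in these outcomes" and plans, within the intervention arm, a regression of each outcome on the number of activities, adjusted for the baseline score of the same outcome.

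SAP 7.3 replaces that regression with five multilevel models and gives their form by reference: "The MLM parameters will be similar to the primary model (described previously". Usage enters in two parts:

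- "Between-person usage will be a Level-2 variable, indicating each participant's usage over the entire number of active days in the study"
- "within-person usage will be at Level-1, indicating the amount of app usage (relative to days active) between assessments"

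The equation referred to is in SAP 7.2. Its Level-2 coefficient "denotes the fixed effect of treatment condition (a Level-2 variable"; Time has one fixed slope; and a further term "denotes a random slope for time (allowing each individual to have a unique trajectory". No fixed term lets the slope depend on the Level-2 variable. SAP 5 makes baseline one of the four outcome occasions and lists age, gender and race as covariates. SAP 6 adds auxiliary variables chosen for their relation to missingness. Neither section promises adjustment for the baseline score.

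**The concern.** In the primary model the Level-2 variable is randomised, so baseline level is balanced across it in expectation. Usage is not randomised. Protocol II.c says participants will not be told how often to use the app, so a teen who is more or less stressed before download may use it more or less. If usage takes the place of condition in the 7.2 equation, its coefficient compares heavier and lighter users on a score averaged over visits that include the pre-app one. A difference that existed before download would then be read as a relation between app use and outcome, for any of the five outcomes. A real link with improvement would be diluted by the baseline visit, and it could be cancelled if heavier users start out worse.

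Heavier here means more activities per active day, as 7.3 defines usage. The choice of that ratio and the coding of the within-person term are separate questions.

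**Working it through.** **No figure to reproduce.** The documents give no alpha, SD, usage distribution or expected correlation for this analysis. From the documents: 400 planned in the Happify arm before attrition (protocol III, Sample Size), four visits (SAP 5), and the model form (SAP 7.2, 7.3). Everything else below is assumed.

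**Step 1: what the coefficient estimates.** With usage in the 7.2 equation, the GLS coefficient is a weighted mean of the four visit-specific usage-outcome associations, with weights proportional to V⁻¹1.

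- Random intercept only, complete data: 0.25 at each visit.
- Random slope added (assumed intercept SD 4.5, residual SD 4 and slope SD 1 PSS point per visit, baseline coded 0): 0.36, 0.29, 0.21, 0.14. The pre-app visit now counts most.

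**Step 2: false rejection when usage has no relation to change.** Assume score variance 1, made up of a stable trait (0.5) and independent visit noise (0.5), so the within-person correlation is 0.5. Usage is standardised and has covariance a with the trait and b with the baseline noise, with a + b = 0.10, its correlation with the baseline score. N = 400, two-sided 5%, z = r√N/√(1−r²).

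- *Main effect* (regression of the person mean on usage): covariance a + b/4; variance of the mean 0.5 + 0.5/4 = 0.625; r = (a + b/4)/√0.625.
- *Usage x Time* (regression of the person slope, visit weights −0.3, −0.1, 0.1, 0.3): covariance −0.3b; variance 0.5 × 0.20 = 0.10; r = −0.3b/√0.10.
- *Baseline-adjusted* (mean of the three later visits given baseline): covariance a − 0.5 × 0.10; residual variances 0.6667 − 0.25 = 0.4167 for the outcome and 0.99 for usage; r = (a − 0.05)/√(0.4167 × 0.99).

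| Usage tracks | a, b | Main effect: r, z, rejection | Usage x Time: r, z, rejection | Baseline-adjusted: r, z, rejection |
|---|---|---|---|---|
| Stable trait | 0.10, 0 | 0.126, 2.55, 72% | 0, 0, 5% | 0.078, 1.56, 34% |
| Observed baseline score | 0.05, 0.05 | 0.079, 1.59, 35% | −0.047, −0.95, 16% | 0, 0, 5% |
| Momentary baseline state only | 0, 0.10 | 0.032, 0.63, 10% | −0.095, −1.91, 48% | −0.078, −1.56, 34% |

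Simulation of the same settings agrees within simulation error. It gives 73%, 35% and 10% for the main effect, 5%, 16% and 47% for usage x Time, and 34%, 4% and 34% for baseline adjustment.

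In the trait case the main-effect rate at baseline-score correlations of 0.05, 0.10, 0.15 and 0.20 is 25%, 73%, 97% and about 100% with 400 participants. With 250 it is 17%, 51%, 87% and 98%.

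**Step 3: dilution and masking.** This uses the PSS scale with the SDs in Step 1 (total SD √(4.5² + 4²) ≈ 6). Let each SD of usage bring an extra −0.25 points per visit and be unrelated to starting level. With a random intercept only, the main effect averages 0, −0.25, −0.50 and −0.75, which is −0.375. It rejects in 36% of simulated trials, against 80% for usage x Time. With the random slope the figures are 18% and 68%. Now let heavier users start 0.75 points higher per SD of usage and improve 0.5 points more per visit. The averaged effect is 0.75 − 0.5 × 1.5 = 0. The main effect rejects in 4% (random intercept) to 9% (random slope), and usage x Time in about 100%.

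**Step 4: do the other model terms help?** Adding the within-person usage term left the between-person rejection rate at 93–95%, with no usage effect and usage correlated 0.2 with the stable level. A REML check at the same correlation, with 30% of post-baseline visits missing, rejected in 55 of 60 trials for the main effect and 1 of 60 for usage x Time.

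**The case against.** **The equation is inferred.** The SAP calls the usage models similar to the primary one and prints nothing further, so an unstated product with Time is possible. If the primary equation gained a condition x Time term, the usage models might follow. This stands as a limit: the finding is that no term for differential change is specified, not that one is ruled out.

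**The SAP does not claim to test change with this coefficient.** SAP 3 speaks only of association, and the change hypothesis comes from the protocol. A reader might infer that the SAP ignores change altogether. It does not: the dose-response analysis at the end of 7.3 refers to overall change. That is a separate analysis with a different usage measure, and it does not alter what the between-person coefficient estimates.

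**Other safeguards.** The between/within split protects only the within-person coefficient (Step 4). The check in 7.2 on correlation between random and fixed effects would show little, because a Level-2 main effect absorbs the pre-existing difference itself.

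**The interaction has its own false signal.** This is the strongest point, and it stands. A reader might take usage x Time as a clean test, since it holds 5% when usage tracks the stable trait. It does not hold 5% when usage tracks the observed baseline score (16%) or a bad week at baseline (47%), because of regression to the mean. Entry requires elevated stress and brooding scores, so this is a live possibility. Baseline adjustment is nominal in the middle case and biased in the other two. The documents do not say which case applies.

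**Conclusion.** The concern holds for the model as written. The between-person usage coefficient is a weighted average over all four visits. It is biased as a measure of greater improvement with greater use whenever self-selected usage is related to pre-existing level, and it can dilute or mask a real link.

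The size depends on assumptions. At a usage-baseline correlation of 0.10 with 400 participants, false rejection runs from about 10% to about 73% according to what usage tracks. The direction of the argument does not depend on those values.

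Two stronger readings are not supported. The coefficient will not be significant every time users differ beforehand: even in the trait case the rate is 25% at correlation 0.05. Nor is it blind to improvement: real change moves it in part, but cannot be separated from prior differences.

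The severity is modest. The analysis is exploratory, confined to the Happify arm and observational under any model. The randomised comparison is not touched.

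**What to change.** In SAP 7.3:

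- Print the usage equation, and add between-person usage x Time to each of the five models as the estimate of differential change.
- Report beside it the baseline-adjusted regression from protocol II.e, and state which usage measure it uses, since the protocol's is the count of activities.
- Report the between-person main effect only as a description of how users differ.
- State that neither change analysis is causal and that the two can disagree. Usage x Time is open to regression to the mean when usage tracks the baseline score or momentary state. Baseline adjustment leaves residual bias when usage tracks the stable trait, and is also biased when usage tracks only the momentary state.

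The cost is SAP wording, one extra term in five exploratory models and one further regression per outcome; no new data are needed. The drawbacks are a larger standard error for an interaction than for a main effect, and two estimates to report and reconcile for each outcome.
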